10.6.3. Laboratory measurements

The laboratory measurements to be collected in this study include haematology, clinical chemistry, pregnancy testing (for females of childbearing potential), urinalysis, CRP, ESR and immunological measurements (T-cell subsets). The blood will be drawn and sent to the laboratory in accordance with standard NHS practice.

T-cell samples will be sent for flow-cytometry. Sample labels containing appropriate identification information will be provided.

In addition to the above, a maximum of 40ml of blood will be drawn and stored for exploratory soluble biomarker testing at baseline and week 24. Approximately an additional 25 ml will be collected at visits 2-5.

10.6.4. Annual reports

Annual Safety Report

An annual report describing any relevant safety data related to the trial must be submitted to the main REC, MHRA and the Sponsor within 60 days of the anniversary of the Clinical Trial Authorisation being granted.

This annual safety report should follow the format of a Developmental Safety Update Report (DSUR). A template and guidance for the completion of this report is available from the Sponsor QA Office.

Annual Progress Report

A progress report must be submitted annually to the REC which gave the favourable opinion, following the anniversary on which the favourable opinion was first given.

A copy signed by the CI must be emailed to the REC and Sponsor within 30 days of the end of the reporting period.

10.6.5. End of trial notification and report

Upon completing the trial, as defined in section 6.5.7, an end of trial declaration must be submitted to the MHRA within 90 days of the end of the trial (or 15 days if premature termination) by the Sponsor or Sponsor-delegated individual.

All trial activities (i.e. follow-ups, visits) should be completed before the submission of the end of trial declaration form.

Within one year of the end of trial for non-paediatric clinical trials, the sponsor (or their delegated) will be responsible for uploading the end of trial summary report to EudraCT as per the commission's guidelines on posting and publication of result-related information.

A copy of this end of trial report should also be supplied to all support departments involved in the study, for example pharmacy and or radiology. The CI must review and sign / date the report.

11. STUDY MANAGEMENT AND ADMINISTRATION

11.1. Good clinical practice (GCP) and regulatory compliance

This clinical trial, which involves the use of an investigational medicinal product has been designed and will be run in accordance with the Principles of GCP and the current regulatory requirements, as detailed in the Medicines for Human Use (Clinical Trials) Regulations 2004 (UK S.I. 2004 / 1031) and any subsequent amendments of the clinical trial regulations.

11.2. Adherence to protocol

The Investigator should not deviate from the protocol. In medical emergencies, the Investigator may use his/her medical judgment and may remove a study participant from immediate hazard before notifying the Sponsor, the MHRA and the REC in writing regarding the type of emergency and the course of action taken.

11.3. Monitoring, audit and inspection

The Sponsor reserves the right to audit any site involved in the trial and authorisation for this is given via the study contract or agreement. A site may be audited, by LIRMM, an independent contractor working for LIRMM or may be subject to inspection by the MHRA at any time in order to ensure compliance with ICH-GCP, and the Investigator should allow direct access to trial documentation.

11.3.1. Procedures for monitoring subject compliance

Patients will be asked regarding compliance with treatment at each study visit; diary cards will also be used to support the review of patient IMP compliance.

Members of the research team will review compliance at each clinic visit before returning the diary to the patient. This compliance review will be detailed in the medical notes.

11.3.2. Definition of source data

Source documents are original records in which raw data are first recorded. These may include, e.g. hospital/clinic/general practitioner records, charts, diaries, x-rays, laboratory results, printouts, pharmacy records, care records, or other printouts, completed scales, or Quality of Life Questionnaires. Source documents will be kept in a secure, limited access area.

Some data will be recorded directly in the CRF and will not appear in a physical source document [as defined in the Source Data Location Sheet document].

Source documents that are computer-generated and stored electronically will wherever possible be printed and filed in the patient medical notes for review by the monitor/inspector.

The Investigator will authorize the monitor to compare the content of the print out and the data stored in the computer to ensure all data are consistent. If electronically stored and impractical to print, each timely review of the electronically stored data will be annotated in the patient's notes.

Electronic data records such as x-ray and ultrasound records will be saved and stored in an appropriately secure location as described in the Source Data Verification form

11.3.3. Source data verification

Source data verification ensures accuracy and credibility of the data obtained. During monitoring reported data are reviewed with regard to being accurate, complete, and verifiable from source documents (e.g. subject files, recordings from automated instruments, x-ray films and laboratory notes). All data reported on the CRF should be supported by source documents, unless otherwise specified in section 11.3.2. Data Verification and will be carried out by the investigators and members of the study team who will check the case report forms for completeness and clarity, and crosscheck them with source documents.

11.3.4. Quality assurance

Investigators will promptly notify the Sponsor Quality Assurance Office of the following within the required timeframe:

- Serious breaches of GCP
- Urgent safety measures
- Protocol violations
- Any amendments to the trial
- Any changes the Clinical Trial Risk Assessment (form A).
- Any other issues as stated in the study contract or agreement

11.3.5. Trial oversight

The trial will be overseen at all times by the Sponsor, The University of Leeds. It is expected that the joint Sponsor office will monitor and audit the study on in accordance with the trial-specific monitoring plan (TMP). A copy of the TMP can be found filed in the Trial Master File. The local study team will have day-to-day oversight, led by the PI.

The research team will also utilise the in-house Clinical Trials Associate to routinely monitor the study (also see TMP). The study will also be discussed at regular trial update meetings to review any issues or potential concerns. The trial research team can then feed back to the trial steering committee where required.

11.3.6. Trial steering committee (TSC)

Independent oversight of the study will be conducted by the Trial Steering Committee. Amongst its members will be an independent chair (clinician), a clinician who is independent of the study research team, and a representative of the LIRMM study management team. Additional members may be appointed at the discretion of the CI. They are expected to meet at least six-monthly.

Trial Steering Committee Terms of Reference:

Specifically, the Trial Steering Committee will be responsible for monitoring the following:

- I. Patient Safety
- II. Adherence to Protocol
- III. To monitor and supervise the progress of the trial towards its interim and overall objectives.
- IV. To review and consider, at regular intervals, new and relevant information from other sources (e.g. other related trials).
- V. In light of any significant issues, concerning any of the above, to inform the Sponsor on the progress of the trial.

11.4. Data handling

11.4.1. Electronic CRF completion

The research team is responsible for prompt reporting of accurate, complete, and legible data in the eCRF and in all required reports.

Any change or correction to the electronic CRF will be time-stamped and documented within the data storage system, with all previous versions of the form being retained for future reference.

The Investigator will maintain a list of personnel authorized to enter data into the CRF.

11.4.2. Database entry and reconciliation

Source data will be transcribed into the eCRF, which also incorporates a validated electronic database, using a research data management system (MACRO). Computerized data cleaning checks will be used in addition to manual review to check for discrepancies and to ensure consistency of the data. Data will be entered into the research database using a rolling query-resolution system designed to identify data entry errors and protocol deviations in a timely fashion to allow accurate reconciliation.

An electronic audit trail system will be maintained within the MACRO system to track all data changes in the database once the data has been saved initially into the system or electronically loaded. Regular backups of the electronic data will be performed.

11.4.3. Screening and enrolment logs

Subject's Screening will be recorded in the Subject Screening Log.

The Investigator will keep a list containing all subjects enrolled into the study. This list remains with the Investigator and is used for unambiguous identification of each subject. The list contains the subject identification number, full name, date informed consent signed, date of screening, and the hospital number or National Health Security number, if applicable.

The subject's consent and enrolment in the study must be recorded in the subject's medical record. These data should identify the study and document the dates of the subject's participation.

11.5. Archiving and data retention

In line with the principles of GCP / UK Clinical Trial Regulations, at the end of the trial, essential documents will be securely archived at each participating centre for a minimum of 25 years. However, because of international regulatory requirements, the Sponsor may request retention for a longer period. Arrangements for confidential destruction will then be made. If a patient withdraws consent for their data to be used, it will be confidentially destroyed

immediately. No records/study documentation/data may be destroyed without first obtaining written permission from the Sponsor.

Essential documents include (this list is not exhaustive):

- Signed informed consent documents for all subjects.
- Subject identification code list*, screening log (if applicable) and enrolment log.
- Record of all communications between the Investigator, the REC and the Sponsor.
- Composition of the REC, and the Sponsor (or other applicable statement as described in section 13.6).
- List of sub-investigators and other appropriately qualified persons to whom the Investigator has delegated significant trial-related duties, together with their roles in the study and their signatures.
- Copies of case report forms and documentation of corrections for all subjects.
- Investigational product accountability records.
- Record of any body fluids or tissue samples retained.
- All other source documents (subject medical records, hospital records, laboratory records, etc.).
- All other documents as listed in section 8 of the ICH E6 Guideline for Good Clinical Practice (Essential Documents for the Conduct of a Clinical Trial).

*European Union legislation requires this list to be maintained for a minimum of 15 years.

Normally, these records will be held in the Investigator's offsite archives.

If the Investigator is unable to meet this obligation, he or she must ask the Sponsor for permission to make alternative arrangements. Details of these arrangements should be documented.

11.6. Study suspension, termination and completion

Suspension or termination of the study may occur at any time for any reason, following discussion between the Investigator and the Sponsor. In the case of early study termination, the Sponsor or delegated individual will be responsible for completing a premature end of study report to the Medicines and Healthcare products Regulatory Agency (MHRA) and the Research Ethics Committee (REC) within 15 days. Upon study completion, the Sponsor or Sponsor-delegated individual will be responsible for sending the Declaration of the End of a Clinical Trial to the MHRA within 90 days. The Sponsor or Sponsor-delegated individual will be responsible for providing the end of trial report to the MHRA within 1 year of the end of the trial.

12. DATA EVALUATION

12.1. Responsibilities

The trial statistician will be responsible for producing the final data report.

12.2. Hypotheses

The primary alternative hypothesis is that the difference (Δ) in the proportions of patients in clinical remission (DAS28 ≤ 2.6) after 6 months of first-line treatment with MTX monotherapy between those with normal (Arm A) vs. abnormal (Arm B) naive CD4 $^{+}$ T-cell frequencies will differ from 0.

$$H_0: \Delta = 0$$

$$H_1: \Delta \neq 0$$

12.3. General statistical considerations

Unless otherwise specified, the last valid measurement before study medication administration will be utilized as the baseline value. In general, summary statistics [n (number of available measurements), arithmetic mean, standard deviation, median, minimum, and maximum] for quantitative variables and absolute and relative frequency tables for qualitative data will be presented.

Wherever possible the trial will be reported in accordance with the recommendations of the CONSORT (Consolidated Standards of Reporting Trials) statement.

This trial includes both a confirmatory comparison (arm A vs arm B) and a pilot comparison (arm B vs arm C). For comparisons between arms A and B, two-tailed significance tests will be conducted at the 5% level of significance. Comparisons between arms B and C will be purely descriptive.

A detailed statistical analysis plan (SAP) will be completed prior to the final lock of the database; any differences between the final analysis and the SAP will be documented in the trial report.

12.4 Analysis sets

Full analysis set (FAS): The FAS will include all patients randomised. Following the intent-to-treat principle, patients will be analysed according to the treatment assigned irrespective of treatment received.

Per protocol set (PPS): The PPS will include patients in the FAS who have no significant deviations from the protocol that may influence the viability of the data.

Safety set: The Safety set will include all patients who took at least 1 dose of study treatment during the treatment period. Patients will be evaluated according to study treatment received.

12.5. Planned efficacy analyses

12.5.1. Primary endpoint analysis

The primary endpoint analysis will be conducted in the FAS. Binary logistic regression will be used to compare the proportion of patients achieving clinical remission at 6 months between arms A and B, adjusting for DAS28 at baseline. Both unadjusted and adjusted odds ratios will be presented, together with 95% confidence intervals.

12.5.2. Secondary endpoint analyses

Secondary endpoint analyses will be conducted in the FAS. The proportions of patients in clinical and imaging remission at 3 & 6 months will be compared between arms A and B in the same manner as the primary analysis (analyses of imaging remission will adjust for the number of joints scoring PD>0 at baseline).

Patient-reported outcomes at 3 and 6 months will be compared between arms A and B using non-parametric quantile (median) regression, controlling for baseline values in each case. Unadjusted and adjusted differences will be presented, together with 95% confidence intervals.

For comparisons between Arms B and C, descriptive summaries of all endpoints will be presented within each arm. Unadjusted and adjusted between-group differences and a range of 90% confidence intervals (75%, 85%, 90%, 95%) will be presented but no inferential tests will be conducted. Assuming preliminary proof of concept is obtained (i.e. the proportion of patients in clinical remission at 6 months is higher in arm C than arm B), sample size

calculations will be performed for a range of plausible and clinically meaningful between-group differences

12.5.3. Other analyses

Sensitivity analyses of the primary and secondary outcomes will be repeated in the per protocol set.

Previously published research suggested that the optimal naive CD4 T-cell frequency cut-off for prediction of response to MTX monotherapy was equivalent to the expected value for the patient's age. We will verify this by pooling the patients in arms A and B and using non-parametric ROC curve analysis, taking clinical remission at 6 months as the reference variable and age-corrected baseline naive CD4 \pm T-cell frequency as the classification variable. Area under the ROC curve and the 95% confidence interval will be presented. The point at which the Youden Index ($J = \text{sensitivity} + \text{specificity} - 1$) is maximised will be chosen as the optimal cut-off. We will additionally investigate whether there is evidence that baseline DAS28 affects the accuracy of classification by including it as a covariate in a secondary ROC analysis.

12.6. Safety analyses

Safety analyses will be conducted in the safety set. Line listings of all SAEs will be provided in the end of trial report. The frequency of all SAEs during the study period will be presented for each treatment group separately. The data will be displayed as number of subjects experiencing the SAEs, percentage of subjects, and number of SAEs. Data will also be corrected for exposure by 100 patient-years.

12.7. Handling of dropouts and missing data

Wherever possible, patients who discontinue study treatment will continue to be followed up according to the study visit schedule. Patients who discontinue study treatment early due to lack of efficacy will be considered non-responders from that point onward (not achieving clinical or imaging remission). In the main analysis, patients with missing data for reasons other than lack of efficacy will also be considered non-responders; sensitivity analyses will include best-case and worst-case single imputation for these patients, complete case analysis and, if possible, multiple imputation. For patient-reported outcomes, the primary analysis will only include patients with data available; sensitivity analyses will include best-case and worst-case single imputation for patients with missing data and, if possible, multiple imputation.

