12.9. Determination of sample size and randomization method

We will allocate the patients to arm A if the patient's naive CD4⁺ T-cell frequency is normal for their age and gender. In our previous pilot study 42% of comparable RA patients had abnormal frequency values, of whom 25% responded to MTX at 6 months compared to 68% of those with normal values. Those with abnormal values will be (randomly permuted block) randomised 1:1 to arm B or C, therefore this would result in an approximate 2.75:1 ratio of patients in arms A and B. For the primary outcome of clinical remission at 24 weeks, at the 5% level of significance, to achieve 80% power to detect a difference between the target proportions of patients achieving clinical remission in arms A (68%) and B (25%)[25], a total of 53 patients would be required, assuming binary logistic regression with a variance inflation factor of 1.05 estimated from pilot data. We will increase the sample size to n=60 to account for 10% drop-out. The total number needed to be recruited to the study would therefore be 76 (44 in arm A, 16 in arm B and 16 in arm C).

To have a more robust estimate of the proportion of clinical remission in arm B and C, recruitment will continue until at least 34 and no more than 60 patients with abnormal T-cell values have been randomised 1:1 to arm B or C, and there are at least 46 patients in arm A. Thus the total sample size for the study is anticipated to be between 76 (approximately A=44, B=16, C=16) and 106 patients (approximately A=46, B=30, C=30). In the case where recruitment within Arm A is disproportionately recruiting more than Arm B or C, recruitment will stop within Arm A once minimum recruitment number has been reached. Patients will not be disadvantaged as they will still receive Treat to Target care.

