# 7. Outcomes

## 7.1 Primary outcome

The primary outcome is the difference in the proportions of patients in clinical remission at 24 weeks of first-line methotrexate with T2T care between those with normal (Arm A) vs. abnormal (Arm B) naïve CD4+ T-cell frequencies at baseline.

The Disease Activity Score (DAS28ESR) is a combined index that measures disease activity in patients with Rheumatoid Arthritis (RA). It has been extensively validated for its use in clinical trials. It incorporates the tender 28-joint count (TJC28), the swollen 28-joint count (SJC28), erythrocyte sedimentation rate (ESR; mm/hour) and patient global/general health assessment VAS (mm).

The TJC28 and SJC28 are calculated from the assessment of the same 28 joints where each joint is determined to be either tender or not tender and either swollen or not swollen. The assessment will be performed by an independent assessor to minimize bias. Where possible, the same assessor should preferably perform the TJC and SJC for a given patient particularly during the study to minimize inter-observer variation.

Missing joint assessments will typically result in a missing count, however there are several cases of this (see CTT20 'multiple IJA missed entry') where they will be imputed as 0 due to confidence

expressed by the PI that the missing CRF fields should have indicated that the joint was not affected. In most of these cases only a few assessments were missing per participant.

The formula for DAS28(ESR) is:

$$DAS28(ESR) = 0.56\sqrt{TJC28} + 0.28\sqrt{SJC28} + 0.014(GH) + 0.70\ln(ESR)$$

The DAS28ESR will automatically be calculated within the MACRO system and computed at the analysis stage from the stored DAS28ESR components. Note that ESR values of 0 will be input as 0.001 to allow for them to be compatible with the DAS28 formula (i.e.  $\ln(0)$  is undefined). The DAS28ESR ranges from 0-10 with higher scores indicating greater disease activity. If any of the components are missing, then DAS28ESR will be missing. Clinical remission (primary endpoint) will be deemed to have been achieved if  $DAS28ESR \leq 2.6$ .

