### 11.5.1 Primary analysis

The estimand for the primary outcome is the difference in the proportion of patients in clinical remission (DAS28ESR  $\leq 2.6$ ) at 24 weeks of first-line methotrexate with T2T care between those with normal (Arm A) vs. abnormal (Arm B) naïve CD4+ T-cell frequencies, with patients who discontinue study treatment early due to lack of efficacy considered as treatment non-responders.

The primary endpoint will be analysed using binary logistic regression in the FAS. The model will adjust for DAS28ESR at baseline, age (at baseline), gender, smoking status (binary; current or previous vs never), and trial arm. Participants with missing data will be imputed as treatment non-responders.

The treatment effect will be presented in the form of both unadjusted and adjusted odds ratios, along with the corresponding two-sided 95% Wald CIs and p-values. Model coefficients for the covariates with 95% Wald CIs will additionally be presented to aid understanding of the fitted model. The model coefficients will be used to calculate the marginal proportions and difference in proportions. Two-sided bias-corrected 95% CIs will be calculated via non-parametric bootstrapping.

Model assumptions will be checked as follows: the multicollinearity between variables can be checked using the variance inflation factor (VIF), which measures the correlation and strength of correlation between the predictor variables in a regression model. Checks for influential observations and outliers will be conducted using Cook's Distance and if any are detected then sensitivity analyses will be completed to assess the impact on the model when these observations are removed. Graphs will be plotted of each explanatory variable against the logit of the response variable to assess if the relationship between them is linear. Transformations of the variables included in the model may be considered. If assumptions are not met, appropriate non-parametric tests will be considered.

If the model does not converge then smoking status will be removed from the model. If there are still issues with convergence, resulting in a sparse dataset and complete/ quasi-separation, then Firth logistic regression [4] may be used instead. This is similar to the logistic regression model but includes a penalisation term in the likelihood function.

Table templates for the primary outcome descriptive summaries and results are given in appendix 1.

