## 13 SAP amendment log

Amendment/addition to SAP and reason for change	New version number, name and date
SAP completed and signed-off	V1.0, [name] , 30/01/2025
Section 7.1 and 11.5.1.1- Addition that missing joint assessments listed in CTT20 'multiple IJA missed entry' will be imputed as 0 in the main analysis models due to the confidence of the PI that these are most likely 0 and the large number of participants this impacts.	V2.0, [name] , 12/05/2025
Section 13.1: Changes to protocol analyses added	
Section 11.2 Changes to definition of FAS added Section 13.1: Deviation from protocol definition of FAS added	V3.0, [name] , 21/05/2025

[figure not shown]

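### An incomplete DAS28ESR at an attended Week 24 visit is scored as non-remission even in the few patterns where the recorded items already guarantee remission

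*Protocol*

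**What the plan says.** The rule has two halves, in different places.

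- **Component rule (SAP 7.1):** "If any of the components are missing, then DAS28ESR will be missing". The same section says that a blank joint item normally makes the whole joint count missing. The joints on the CTT20 deviation list are the exception and are set to 0 in the main analysis. The SAP amendment log gives two reasons: the investigator's confidence that they were unaffected, and "the large number of participants this impacts".
- **Outcome rule (Protocol 12.7):** "In the main analysis, patients with missing data for reasons other than lack of efficacy will also be considered non-responders". SAP 11.2.3 repeats this, and SAP 11.5.1 applies it to the primary model: "Participants with missing data will be imputed as treatment non-responders".

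Neither half separates an attended visit with one blank item from a visit that never took place. SAP 11.5.1.1 plans best-case and complete-case analyses, with multiple imputation as an option. It also plans a missing-joint sensitivity analysis that turns the CTT20 zeros back into missing values and hence into non-response.

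**The concern.** The endpoint is DAS28ESR at or below 2.6. A patient whose score stays at or below 2.6 for every possible value of the blank item meets that definition, so scoring a failure is a known misclassification and not a cautious guess. The estimand in SAP 11.5.1 names one kind of failure by definition, stopping treatment early for lack of efficacy, and a blank VAS line or joint box is not that.

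The error goes one way: a true non-remitter is scored correctly, and only a true remitter can be moved. At stake are a remission rate biased downwards in the primary analysis and a joint sensitivity analysis that looks harsher than the data require. Other variables do have partial-data rules (HAQ-DI in SAP 7.2.2, CRP below detection in SAP 11.2). For the primary endpoint there is only the CTT20 exception.

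**Working it through.** **Inputs.** Formula from SAP 7.1: DAS28ESR = 0.56√TJC + 0.28√SJC + 0.014·GH + 0.70·ln(ESR), with remission at ≤2.6. Ranges from Protocol 4.2: GH 0–100 mm, joint counts 0–28. Planning rates 68% (A) and 25% (B), ratio 2.75:1 and variance inflation 1.05 from Protocol 12.9. Two-sided 5% from Protocol 12.3.

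**Step 1. The plan's own sample size.** Pooled proportion = (0.25 + 2.75×0.68)/3.75 = 0.565.

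n(B) = [1.96·√(0.565×0.435×(1+1/2.75)) + 0.842·√(0.25×0.75 + 0.68×0.32/2.75)]² / 0.43² = 13.32.

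Total 13.32×3.75 = 49.94; ×1.05 = 52.43, rounded up to the stated 53. The sample size is not in question.

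**Step 2. When do the recorded items prove remission?** Set the blank item to its maximum and solve for the highest ESR that keeps the score at 2.6: ESR limit = exp[(2.6 − recorded part without ESR − maximum of blank item)/0.70].

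| Blank item | Maximum it adds | Other items | ESR limit | Provable at whole-number ESR |
|---|---|---|---|---|
| GH | 1.40 | TJC 0, SJC 0 | 5.55 | ≤5 |
| GH | 1.40 | TJC 0, SJC 1 | 3.72 | ≤3 |
| GH | 1.40 | TJC 1, SJC 0 | 2.49 | ≤2 |
| Whole SJC | 0.28√28 = 1.48 | TJC 0, GH 0 | 4.94 | ≤4 |
| Whole SJC | 1.48 | TJC 0, GH 20 | 3.31 | ≤3 |
| Whole TJC | 0.56√28 = 2.96 | SJC 0, GH 0 | 0.60 | none at ESR ≥1 |
| One joint, both items | 0.84 | other 27 clear, GH 0 / 10 / 20 | 12.4 / 10.1 / 8.3 | ≤12 / ≤10 / ≤8 |
| One joint, swelling only | 0.28 | all else clear, GH 10 | 22.5 | ≤22 |
| One joint, tenderness only | 0.56 | all else clear, GH 10 | 15.1 | ≤15 |

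A wholly missing TJC could be settled only by an ESR recorded as 0, which SAP 7.1 enters as 0.001. A missing ESR never proves remission: the documents give no upper limit, and with every other item at 0 the score passes 2.6 once ESR exceeds exp(2.6/0.70) = 41.0.

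Two examples:
- TJC 0, SJC 0, ESR 5, GH blank: 0.70·ln 5 = 1.13, so the score lies between 1.13 and 1.13 + 1.40 = 2.53.
- 27 joints clear, one joint blank for both items and not on the CTT20 list, GH 10, ESR 10: 0.14 + 1.61 = 1.75, up to 1.75 + 0.84 = 2.59.

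Both patients are in remission whatever the blank was. The plan scores both as failures.

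**Step 3. The missing-joint sensitivity analysis.** With the CTT20 joints reset to missing, the second example becomes a failure there even if its joint is on the list. Each patient moved in this way changes the arm's rate by 1/44 = 2.3 points in Arm A or 1/16 = 6.3 points in Arm B at the minimum sizes. The number of listed patients by arm is not given.

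**Step 4. Size in the main analysis.** The documents give no rate, so I assume that a share s of true remitters is both incomplete and provable, equal in both arms. Power is an exact enumeration of the unadjusted two-sided Wald test of the log odds ratio at 44 vs 16, counting tables with an empty cell as not significant and leaving out covariates and variance inflation.

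| s | Arm A rate | Arm B rate | Difference | Remitters lost, A / B | Power |
|---|---|---|---|---|---|
| 0 | 68.0% | 25.0% | 43.0 | 0 / 0 | 85.1% |
| 0.5% | 67.7% | 24.9% | 42.8 | 0.15 / 0.02 | 84.7% |
| 2% | 66.6% | 24.5% | 42.1 | 0.60 / 0.08 | 83.5% |

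**The case against.** The case for leaving the rule alone is substantial.

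- **The provable set is narrow.** This stands. With GH blank it needs an ESR of about 5 or less, and the second example above would fail at GH 11 (2.61). A reader might infer that any missing component hides known remitters. For ESR and for the whole tender count this is not so.
- **The reported gaps are already handled.** A reader might take the amendment log to show that many patients are scored as failures in the main analysis because of blank joints. It shows the opposite: the listed joints are set to 0 there. No passage reports a missing GH, a missing ESR or an unlisted blank joint at Week 24. The log bears on the sensitivity analysis, where the same patients do become failures.
- **Other planned analyses expose the effect.** Partly true. Best-case imputation scores every provable remitter correctly, and complete-case analysis removes them. But best case also makes responders of patients whose status is unknown, and neither analysis uses the recorded items to tell the two groups apart.
- **Visit windows may fill a gap.** SAP 11.2.2 takes the closest non-missing assessment in the window, and the Week 24 window runs from day 128. This covers an in-window ESR if the rule is applied per component, so no separate ESR rule is needed.
- **The bias is conservative.** This holds if the same share of remitters is lost in each arm. It lowers the urgency but does not make a known misclassification correct.

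**Conclusion.** The point holds in a limited form. The two rules together count as failures some patients whose recorded items guarantee remission, and the missing-joint sensitivity analysis carries the same error. In the main analysis the effect is probably small: under the assumed 0.5% to 2%, less than one patient is lost in Arm A and at most 0.08 in Arm B, with power down by 0.4 to 1.6 points. The effect in the sensitivity analysis may be larger, but the documents do not allow it to be sized.

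Two stronger conclusions are tempting. A reader might put the power loss at several points, by taking 5% or 10% of remitters with any missing item as lost. That is the cost of non-responder imputation in general, not of misclassifying provable remitters. A reader might also infer that the loss falls mostly in Arm A. Arm A would have more remitters by count at the planning rates and arm sizes, but with equal missingness the proportion lost is the same in both arms, and the documents give no missingness by arm.

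The change is still worth making, because it corrects only known errors and costs little.

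**What to change.** In SAP 7.1 and 11.2.3, add a bounding rule for an attended Week 24 visit with a missing GH or joint item:

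1. Compute DAS28ESR at the lowest and highest possible value of the blank item (GH 0 and 100 mm; each blank joint item 0 and 1).
2. If both results are at or below 2.6, score remission. Otherwise keep non-responder imputation.
3. Leave the rule unchanged for patients with no Week 24 assessment, and keep patients who stopped for lack of efficacy as non-responders.

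Use the same bounding in the missing-joint analysis of SAP 11.5.1.1, so that a CTT20 case is a failure only where the blank joints leave the status undetermined or above 2.6. Report by arm how many cases were settled in this way. Add no separate ESR substitution; SAP 11.2.2 already maps the closest in-window assessment. Protocol 12.7 needs at most a cross-reference.

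The cost is a slightly longer endpoint derivation and no new data.
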